**Ketone monitoring:**

Blood or urine ketones are checked when BG readings are > 250 or with complaints of illness. Blood ketone results are preferred when a camper is on Depokote, and cases of suspected diabetes ketoacidosis.

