#### **V. e. Response to Hypoglycemia**

- All subjective symptoms of hypoglycemia will be investigated with a capillary BG using a HemoCue meter.
- Volunteers in both of the study arms (closed-loop and usual care) will take carbohydrates to treat hypoglycemia or symptoms consistent with hypoglycemia according to a protocol modified from the usual camp protocol as follows:
- Mild hypoglycemia (mild signs and symptoms or BG 60–80 mg/dl, able to self treat):
  - Wait 15–20 minutes and recheck BG
  - If BG is still < 70 give 15 gm of rapid-acting carbohydrates (glucose tabs, juice, milk, gel, etc.)
- The modified hypoglycemia protocol is intended to allow auto-treatment of mild hypoglycemia with glucagon by the control algorithm to occur without being preempted by carbohydrates given prior to the onset of hypoglycemia (for instance in the 70-80 mg/dl range) or when hypoglycemia is mild (BG 60-70 mg/dl). In order to maintain safety, a second BG check in 15-20 minutes is included so that hypoglycemia is treated if not averted by the closed-loop system.
- For experimental validity, the same modifications from camp policy need to be used for both the closed-loop and open-loop arms of the study. Note that treatment of BG < 60 mg/dl will be according to the normal camp protocol in both arms (immediate treatment with rapid-acting carbohydrates) AND subjects may take carbohydrates at any time for symptoms when BG is < 80 mg/dl
- Camp healthcare providers and camp counselors will carry rapid acting and complex carbohydrate interventions with them at all times. All carbohydrate treatments for hypoglycemia will be documented by study staff (amount and time).
- In any case in which two rapid-acting carbohydrate interventions must be administered by camp protocol or if glucagon is administered manually by injection, a study staff member will check the operation of the bionic pancreas system. Consideration will be given to replacing the glucagon infusion set and/or recalibrating the CGM.

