#### **V. f. Response to Hyperglycemia**

- Any time a ketone check is mandated by camp protocol the closed-loop system will be checked for any malfunction and any such problems will be corrected. The insulin infusion set will be replaced if mandated by camp protocol or if there is any doubt as to its proper functioning.
- If no correctable fault is found, but there is doubt regarding the correct function of the bionic pancreas system, an entirely new backup bionic pancreas system may be started.
- While the new system is being replaced and calibrated the volunteer will use their own pump in open loop mode according to usual care camp protocols.
- If the blood ketone result is  $\geq 0.6$ mmol/dL a study physician or nurse practitioner will be notified and will evaluate the volunteer in person.

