**Secondary endpoint analyses - BG:**

- All of following metrics will be generated from the HemoCue data during the closed-loop period and the usual care period, and the difference between the two periods will be reported unless otherwise specified:
- Average BG as determined from all HemoCue measurements taken during the day/nighttime including all extra measurements taken before meals, taken during exercise, and taken for hypoglycemia monitoring.

- Percentage of the above subset of BG values less than 70 mg/dl.
- Average BG as determined from the pre-meal, before bed, 12:00 AM, and 3:45 AM HemoCue measurements (6measurements per day)
- Percentage of the above subset of BG values less than 70 mg/dl.
- Percentage of subjects with mean BG < 154 mg/dl using all BG values
- Difference in the percentage of subjects with mean BG < 154 mg/dl using before meal and before bedtime BG values only
- Percentage of study days with mean BG < 154 mg/dl
- Number of hypoglycemic events as determined from all HemoCue measurements
- Nadir BG for each hypoglycemic event as determined from HemoCue measurements
- Fraction of scheduled BG measurements within each of the following glucose ranges as determined from all HemoCue measurements :
  - < 70 mg/dl
  - 70-120 mg/dl
  - 70-180 mg/dl
  - >180 mg/dl
  - >250 mg/dl
- Risk of hypoglycemia and hyperglycemia >180 mg/dl and >250 mg/dl during hours with vs. without bionic pancreas downtime
- Difference of outcome measures on day 1 vs. remaining days (days 2-5) and on day 1-2 vs. on remaining days (days 3-5)
- Difference in average BG as determined from the pre-meal, before bed, and 12:00 AM measurements between the non-participants and the open-loop and closed-loop arms.
- Percentage of the above subset of BG values less than 70 mg/dl between the non-participants and the open-loop and closed-loop arms.
- Difference in the percentage of subjects with mean BG < 154 mg/dl using before meal and before bedtime BG values only between the non-participants and the open-loop and closed-loop arms.
- Number of hypoglycemic events as determined from all BG measurements
- Nadir BG for each hypoglycemic event as determined from BG measurements
- Fraction of scheduled BG measurements within each of the following glucose ranges as determined from all BG measurements :
  - < 70 mg/dl
  - 70-120 mg/dl
  - 70-180 mg/dl
  - >180 mg/dl
  - >250 mg/dl

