### **Secondary endpoint analyses – CGM:**

- All of following metrics will be generated from the DexCom G4 Platinum CGM data during the closed-loop period and the usual care period, and the difference between the two periods will be reported unless otherwise specified. Each of these measures will be calculated for the entire period and separately for the full day and for the nighttime (11:00 PM to 7:00 AM).
- Mean CGMG
- Number of CGMG events < 70 mg/dl (episodes separated by < 15 minutes will be considered a single episode) and nadir for each
- Fraction of time spent within each of the following glucose ranges:

- < 70 mg/dl
- 70-120 mg/dl
- 70-180 mg/dl
- >180 mg/dl
- >250 mg/dl
- Area over the curve and below 70 mg/dl (measure of total hypoglycemia exposure)
- Area over the curve and below 50 mg/dl (measure of significant hypoglycemia exposure)
- Percentage of subjects with mean CGMG < 154 mg/dl
- Percentage of study days with mean CGMG < 154 mg/dl
- Mean CGMG in the four hour period following meals
- Mean CGMG during exercise (more active periods, periods of activity greater than walking intensity based on accelerometer data)
- Number of incidents of hypoglycemia and nadir CGMG during exercise
- Correlation between exercise intensity (based on accelerometer data) and likelihood of a hypoglycemic event by CGMG
- Risk of hypoglycemia and hyperglycemia >180 mg/dl and >250 mg/dl during hours with vs. without bionic pancreas downtime (closed-loop period only)
- Mean absolute relative deviation (MARD) of CGM vs. scheduled HemoCue BG measurements
- Standard deviation of CGM values
- Standard deviation of CGM values at night (11:00 PM to 7:00 AM)
- MARD vs. all HemoCue BG measurements Additional accuracy measures using all of the HemoCue measurements as the standard. Statistics will include:
- Median, quartiles, and mean absolute relative difference (MARD) and mean absolute difference (MAD) between CGM and BG reported separately in hypoglycemic (< 70 mg/dl), normoglycemic (70-120 mg/dl), postprandial target (70-180 mg/dl), hyperglycemic (> 180 mg/dl and > 250 mg/dl) ranges.
- Pearson and Spearman correlation coefficient between CGM and BG values reported separately in each range (hypoglycemic, normoglycemic, hyperglycemic).
- Intercept and slope of best-fit line for CGM to BG correlation plots

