### **Secondary endpoint analyses – Non-glycemic:**

- All of following metrics will be generated from the closed-loop and usual care periods and the differences will be reported unless otherwise specified:
- Number of carbohydrate interventions for hypoglycemia (day and night)
- Total number of grams of carbohydrate taken for hypoglycemia (day and night)
- Insulin total daily dose
- Mean daily basal insulin dose
- Mean daily bolus insulin dose
- Number of carbohydrate interventions for hypoglycemia during the daytime (7:00 AM – 11:00 PM)
- Total number of grams of carbohydrate taken for hypoglycemia during the daytime ((7:00 AM – 11:00 PM)
- Number of carbohydrate interventions for hypoglycemia overnight (11:00 PM – 7:00 AM)
- Total number of grams of carbohydrate taken for hypoglycemia overnight (11:00 AM – 7:00 AM)
- Mean meal carbohydrate content
- The following metrics will be generated from the closed-loop period:
- Insulin lispro dosing (u/kg/24 hours)
- Glucagon dosing (mcg/kg/24 hours)
- Fraction of time bionic pancreas in open-loop mode due to loss of CGM signal
- Fraction of time bionic pancreas completely off-line
- Fraction of time bionic pancreas off-line or not functioning properly for each of the following reasons: system crash, communication problem between CGM and bionic pancreas, communication problem between bionic pancreas and pumps, pump malfunction, tubing occlusion, infusion set failure/pulled out
- Difference in mean insulin dose per hour during periods of normal operation vs. periods of bionic pancreas downtime
- Fraction of bionic pancreas downtime during which automatic basal rate suspended or reduced
- Difference in mean insulin dosing during the four hour period after a meal during periods of normal operation vs. periods of bionic pancreas downtime (open-loop dosing)
- Difference of outcome measures on day 1 vs. remaining days (days 2-5) and on day 1-2 vs. on remaining days (days 3-5)
- All of following metrics will be generated from the closed-loop, usual care periods, and from the non-participants and the differences will be reported unless otherwise specified:
- Number of carbohydrate interventions for hypoglycemia (day and night)
- Total number of grams of carbohydrate taken for hypoglycemia (day and night)
- Insulin total daily dose
- Mean daily basal insulin dose
- Mean daily bolus insulin dose
- Number of carbohydrate interventions for hypoglycemia during the daytime (7:00 AM – 11:00 PM)

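### The downtime contrasts for hyperglycemia, mainly above 250 mg/dl, are open to reverse causation because a glucose at that level itself prompts the system check that can lead to downtime

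*Combined protocol and SAP*

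**What the plan says.** Section VI. b lists the contrast twice. Under the CGM secondary analyses it is "Risk of hypoglycemia and hyperglycemia >180 mg/dl and >250 mg/dl during hours with vs. without bionic pancreas downtime (closed-loop period only". Under the BG secondary analyses it is "Risk of hypoglycemia and hyperglycemia >180 mg/dl and >250 mg/dl during hours with vs. without bionic pancreas downtime", from HemoCue data. The non-glycemic list adds "Difference in mean insulin dose per hour during periods of normal operation vs. periods of bionic pancreas downtime".

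The procedures link high glucose to interruption of the device in these steps:

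- Section V. d. ii, Ketone monitoring: "Blood or urine ketones are checked when BG readings are > 250 or with complaints of illness". The hyperglycemia guidance in the same section sets the check at 250 mg/dl or above. It calls for a pump-site change if ketones are positive or if glucose is still rising on recheck.
- Section V. f: "Any time a ketone check is mandated by camp protocol the closed-loop system will be checked for any malfunction". The insulin set is replaced where camp protocol requires it or where its function is in doubt.
- Section V. f, if no fault is found but doubt remains: "an entirely new backup bionic pancreas system may be started". In the meantime, "While the new system is being replaced and calibrated the volunteer will use their own pump in open loop mode".

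For low glucose, section V. e asks for a check after two rapid-acting carbohydrate treatments or an injection of glucagon, and then says: "Consideration will be given to replacing the glucagon infusion set and/or recalibrating the CGM".

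Section VI. a records the number, timing, duration and reasons of downtime. The listed reasons are all device or component faults. None covers a precautionary replacement with no fault found. The closing paragraph of VI. b names age and gender as the adjustment variables.

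**The concern.** A comparison of hours with and without downtime will be read as exposure followed by outcome. For part of the downtime the plan reverses that order: glucose is already above 250 mg/dl, the system is checked because of it, and the interruption follows. The outcome threshold is the trigger threshold. If the triggering value lies in the same hour as the interruption, it counts as an event during downtime.

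Some downtime with a technical label is affected too. An occlusion or failed infusion set may be recognised only because glucose rose. The excursion then belongs to the fault, but the hours before recognition may be classed as free of downtime.

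These endpoints are the plan's direct estimates of glucose risk during an outage, and section I. d says the results should lead to studies with less supervision. A spurious ratio above 250 mg/dl could be taken as the harm of an outage. A spurious ratio below 1 for low glucose could reassure wrongly. The insulin-per-hour contrast is exposed in the same way, because corrections for the triggering high can fall inside the downtime.

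**Working it through.** The plan gives no figure for these endpoints, and section VI. c says there is no formal power analysis, so there is nothing to reproduce. The check asks what ratio would appear if downtime had no effect at all.

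**Closed form.** Let p0 be the baseline risk of the event in an hour and f the share of downtime hours set off by that same event. If every such hour is positive, the apparent ratio is RR = [f + (1 − f) × p0] / p0.

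- Above 180 mg/dl: the second trial in section I. c had 68% of values in 70–180 mg/dl and 0.7% of time below 70, so p0 ≈ 1 − 0.68 − 0.007 = 0.313. At f = 10%, RR = (0.10 + 0.90 × 0.313) / 0.313 = 1.22. At f = 25%, RR = 1.55.
- Above 250 mg/dl: p0 = 10% is an assumption. At f = 5%, RR = (0.05 + 0.95 × 0.10) / 0.10 = 1.45. At f = 10%, RR = 1.90. At f = 25%, RR = 3.25.

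**Simulation.** Glucose was log-normal and autocorrelated in 5-minute steps, with mean 162 mg/dl (pediatric subjects with adaptive bolus, third trial, section I. c), 7 checks a day, 5 days and 4000 simulated subjects. Downtime had no effect on glucose. The following are assumptions: coefficient of variation 40%, correlation time 3 h, spells of 1 h, technical spells at 0.5 or 2 per day, and the probability that a reading above 250 leads to downtime. In the rows with 2 technical spells per day, readings below 60 also led to downtime with the same probability.

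| Technical spells/day | Trigger probability | Share of spells prompted by glucose | RR >180, by hour | RR >250, by hour | RR <70, by hour |
|---|---|---|---|---|---|
| 0.5 | 0 | 0% | 1.00 | 0.99 | 0.99 |
| 0.5 | 5% | 6% | 1.06 | 1.19 | 0.97 |
| 0.5 | 10% | 12% | 1.09 | 1.38 | 0.88 |
| 0.5 | 25% | 24% | 1.22 | 1.89 | 0.79 |
| 2 | 5% | 2% | 1.01 | 1.05 | 1.02 |
| 2 | 10% | 3% | 1.02 | 1.10 | 1.04 |
| 2 | 25% | 8% | 1.05 | 1.28 | 1.02 |

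Counted by reading instead of by hour, the >250 ratios in rows 2 to 4 are 1.37, 1.71 and 2.56. Adding low-glucose triggers to the 0.5-per-day setting moves the <70 ratio to 1.04 (both triggers 10%), 1.09 (both 25%) or 1.68 (high 10%, low 50%). With 2-hour spells and both triggers at 10%, the >250 ratio is 1.32, against 1.39 with 1-hour spells.

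**After separating causes.** With technical spells only (trigger probability zero), the ratios across the three outcomes, by hour and by reading, are 0.98 to 1.02. When prompted spells exist but are set aside, a small residual remains because they remove high values from the comparison hours. In the most extreme 0.5-per-day row (downtime 2.74% of time, by-reading ratio 2.56), it is 1 + 0.0274 × (2.56 − 1) = 1.04.

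**Clock time.** In the second trial, 192 of 576 h were at night, with 93% of night values in range. Daytime in range is (0.68 × 576 − 0.93 × 192) / 384 = 55.5%. Taking about 7% above 180 at night, the daytime share above 180 is (0.313 × 576 − 0.07 × 192) / 384 = 43.5%. If 80% of downtime fell in daytime (an assumption), the pooled null ratio above 180 would be (0.8 × 0.435 + 0.2 × 0.07) / 0.313 = 1.16. The CGM list asks for a separate night analysis; the BG list does not.

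**The case against.** The case on the other side is substantial, and much of it stands.

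- The chain is conditional. A high reading makes a check mandatory, but a backup system is optional, and a site change follows only positive ketones, a still-rising glucose or doubt about the set. Most listed reasons for downtime are technical. This limits the size of the bias; it does not remove the path.
- A reader might infer that low glucose creates downtime in the same way. The documents do not support that. Section V. e names a check, possible replacement of the glucagon set and possible recalibration, with no system replacement and no move to the volunteer's own pump. Section V. c already has the sets changed every 24 hours.
- A reader might infer that downtime will look harmful on every outcome. That also fails: high-glucose triggers alone push the <70 ratio down to 0.79–0.97. Set failures not yet recognised add risk to the comparison hours, which works against an apparent harm.
- The clock-time figures come from six subjects on an algorithm that was later redesigned, and the CGM list already separates the night. Only the BG contrast lacks the split.
- A stricter repair would count only new excursions from spells that start at 70–180 mg/dl. It would discard set failures in which the excursion is the real harm. It could rarely be applied to about seven HemoCue readings a day, and it fails where CGM values are missing because the sensor was lost. That objection is sound, so this repair is not proposed.
- These are secondary items with no causal claim, and reasons and timing are already recorded. This keeps the priority modest. But the recorded reasons lack the category that matters, and the endpoints do not use them.

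**Conclusion.** The point holds for hyperglycemia, and chiefly for values above 250 mg/dl, where outcome and trigger coincide. With no true effect of downtime, the hourly ratio above 250 could be about 1.05 to 1.9. The ratio above 180 is less affected (about 1.01 to 1.22). For values below 70 the direction depends on the mix of triggers and cannot be stated.

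The range rests on assumed trigger probabilities, spell rates, spell length and glucose variability. It illustrates the size and is not a bound, because the documents do not give the share of downtime prompted by glucose. Nothing here touches the co-primary endpoints or the success criteria in section VI. d. It would be wrong to infer that most downtime is triggered by glucose or that the device comparison itself is biased.

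**What to change.** No clinical procedure needs to change.

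1. **Section VI. a, closed-loop data.** Add a downtime reason for a check or replacement prompted by glucose with no fault found. For set failure or occlusion, record whether it was detected through high glucose.
2. **Section VI. b, BG and CGM lists.** Report the contrast separately for (a) spells with a technical cause not detected through glucose, as the main estimate; (b) set failure or occlusion detected through glucose; and (c) glucose-prompted spells with no fault found. Keeping (b) visible preserves the harm of real set failures.
3. **Time order.** Do not count glucose values at or before spell onset as occurring during downtime. This is not enough alone, because glucose stays high for some time after a trigger; the split by cause does most of the work.
4. **Comparison.** Compare within volunteer, and split the BG contrast by day and night as the CGM list already does.
5. **Labels.** Call the all-spell contrast descriptive, and split the insulin-per-hour contrast by the same causes.

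The cost is wording, one reason code, one detection item and some programming. The main estimate will use fewer spells and have wider intervals, and spells due to sensor loss must rely on HemoCue values.

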In the third trial we also tested the accuracy and reliability of two new CGM devices, the G4 Platinum (DexCom) and the Enlite (Medtronic), in addition to the FreeStyle Navigator, over the full duration of each experiment. Venous BG measurements (Glucoscout, International Biomedical) obtained every 15 minutes ( $n = 4294$  reference values) were paired in time with corresponding CGM glucose measurements. The accuracy and precision of the G4 Platinum outperformed the Navigator, with aggregate mean absolute relative differences (MARDs) of all paired points of  $10.8\% \pm 9.9\%$  and  $12.5\% \pm 12.4\%$ , respectively. Both were significantly different from the Enlite with a MARD of  $18.2\% \pm 16.0\%$ . Data reporting percentages, a measure of reliability, were 99.7% for the G4 Platinum, 99.5% for the Navigator, and 96.9% for the Enlite. The performance of the G4 Platinum represents substantial improvements in accuracy compared to the previous generation DexCom (Seven Plus), while the performance of the Enlite represents only a modest improvement in accuracy compared to the previous generation Medtronic device (Guardian). In our previous comparative trial with  $n = 2360$  reference values (29) these sensors had aggregate MARDs for all paired points of  $16.5 \pm 17.8\%$  and  $20.3\% \pm 18.0\%$  respectively vs.  $11.8 \pm 11.1\%$  for the Navigator. The data reporting percentage of the G4 Platinum also represents a marked improvement from 75.9% for the Seven Plus. These data reveal substantial improvements in performance of CGM devices now available in the US market (see Appendix C.) We conclude that either the Navigator or the DexCom G4 Platinum have sufficient accuracy to drive closed-loop BG control. We have therefore built a mobile bionic pancreas using the DexCom G4 Platinum CGM as the input device.

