**HemoCue Blood Glucose Meter:**

The HemoCue is an FDA approved blood glucose meter with lab-equivalent accuracy. Blood glucose measurements will be obtained via fingerstick with the HemoCue meter per camp schedule during the usual care visit and at least seven times per day during the closed-loop visit. Standard care at camp is for BG to be checked at least six to seven times per day so this will follow a similar regimen with (occasionally) only one to two extra readings per day. HemoCue measurements will also be used to calibrate CGM devices during the usual care and closed-loop study visits.

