**Daily Routine:**

- Breakfast ~7:30 AM on weekdays, 8:00 AM on weekends\*\*
- Activity\*
- Activity\*
- Lunch 12:00PM\*\*
- Activity\*
- Activity\*
- Dinner 5:45 PM\*\*
- Activity\*
- Snack 8:30 PM\*\*
- 12:00 AM BG check (routine)

- 3:00 AM BG check if 12:00 AM check required intervention

\*Activity periods are divided by intensity into More Active and Less Active categories. Campers typically have two More Active and two Less Active periods daily.

\*\*BG checks are done 10–30 minutes before meals/snacks with insulin bolus 10–15 minutes before meals.

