#### **During the monitoring of usual care period:**

- CGMG (CGM glucose) every five minutes from the DexCom G4 Platinum CGM
- HemoCue BG measurements before meals, snacks, bedtime, 12:00 AM and 3:45 AM
- Any additional HemoCue BG values
- Estimated carbohydrate intake (from camp healthcare provider documentation)
- Exercise and activity level (from camp schedule)
- Number of hypoglycemic events and nadir BG for each (from camp healthcare provider documentation)
- Number of carbohydrate interventions for hypoglycemia (from camp healthcare provider documentation)
- Total daily dose of insulin (from insulin pump download)

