- Percent of CGM values meeting International Organization for Standardization (ISO) criteria (< 15 mg/dl difference for BG values < 70 mg/dl, < 20% absolute difference for BG values > 70) in each range.
- Clarke Error Grid Analysis (EGA) for all CGM and BG pairs in hypoglycemic, normoglycemic, post-prandial target, and hyperglycemic ranges. The data will be reported as fraction of values in zones A (clinically accurate), B (benign), zone C (overcorrect), zone D (failure to detect), and zone E (erroneous).
- Continuous Clarke Error Grid Analysis (EGA) for all CGM and BG pairs, including point- and rate-EGA (P-EGA and R-EGA) for each volunteer in hypoglycemic, normoglycemic, post-prandial target, and hyperglycemic ranges. The data will be reported as fraction of values in zones A (clinically accurate), B (benign), zone C (overcorrect), zone D (failure to detect), and zone E (erroneous).
- Reliability index calculated as percent of possible values actually recorded by CGM.
- MARD during periods with and without exercise (by 15 minute periods).
- Difference of outcome measures on day 1 vs. remaining days (days 2-5) and on day 1-2 vs. on remaining days (days 3-5)

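### Rate error-grid analysis for every volunteer and glucose range is not supported by scheduled fingersticks about 2.75 to 5.75 hours apart, and accuracy below 70 mg/dl per volunteer rests on very few pairs

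*Combined protocol and SAP*

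**What the plan says.** Aim 1 (section II) names CGM accuracy as a secondary outcome. Section VI.b, under the CGM secondary analyses, asks for "Continuous Clarke Error Grid Analysis (EGA) for all CGM and BG pairs, including point- and rate-EGA (P-EGA and R-EGA) for each volunteer", in the hypoglycemic, normoglycemic, post-prandial target and hyperglycemic ranges. The same list asks for "MARD during periods with and without exercise (by 15 minute periods" and says that CGM measures are to be calculated for nighttime separately as well.

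The reference is the fingerstick meter: "Additional accuracy measures using all of the HemoCue measurements as the standard". Section VI.a lists what is collected in usual care, "HemoCue BG measurements before meals, snacks, bedtime, 12:00 AM and 3:45 AM", plus any additional values, and gives the same list for the closed-loop period. Section VI.b counts a core set: "Average BG as determined from the pre-meal, before bed, 12:00 AM, and 3:45 AM HemoCue measurements (6measurements per day". Section V.c sets a minimum for one arm: "at least seven times per day during the closed-loop visit". Under Daily Routine in section V.d.ii, "BG checks are done 10–30 minutes before meals/snacks".

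The earlier accuracy comparison in section I.c had a much denser reference: "Venous BG measurements (Glucoscout, International Biomedical) obtained every 15 minutes".

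The plan does not say how a CGM or reference rate is to be computed. It sets no maximum gap between the two fingersticks that form a rate and no minimum number of pairs per volunteer and range, and it does not define which fingersticks count as exercise readings.

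**The concern.** A rate error grid needs two reference readings close enough together that their difference over time describes how fast glucose was moving. Readings hours apart give only an average slope over a span in which glucose may have risen and fallen again. The plan carries over an analysis suited to 15-minute venous sampling and applies it to spot fingersticks, for all pairs, for each volunteer and within each range.

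At stake is a named secondary outcome. A rate grid on these data could be read as evidence about the sensor when it mainly describes the sampling gap. Splitting by volunteer and range also leaves low-range cells that are empty or nearly so, and that is the range where sensor accuracy matters most for safety.

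**Working it through.** **1. Reproduce the plan's count.** Pre-breakfast, pre-lunch, pre-dinner, bedtime snack, 12:00 AM and 3:45 AM make 6 per day, matching section VI.b. Over five days: 6 × 5 = 30 scheduled readings, or 7 × 5 = 35 at the closed-loop minimum. A 15-minute reference gives 96 per day, or 480 over five days.

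**2. Gaps.** Meals are at 7:30, 12:00 and 17:45 and the snack at 20:30 (section V.d.ii). Taking checks 20 minutes before (the stated range is 10–30), the times are 7:10, 11:40, 17:25, 20:10, 0:00 and 3:45.

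| Interval | Gap (min) |
|---|---|
| Breakfast to lunch | 270 |
| Lunch to dinner | 345 |
| Dinner to snack | 165 |
| Snack to midnight | 230 |
| Midnight to 3:45 | 225 |
| 3:45 to breakfast | 205 |

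The mean is 240. Letting the lead time vary over 10–30 minutes moves the extremes by 20 minutes each way, to 145 at the shortest and 365 at the longest. A separate bedtime reading, whose time is not stated, would split one gap.

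**3. Rates these gaps can show.** Reference rate = (BG2 − BG1) / gap. The calibration rule in section V.d.iii treats 1 mg/dl/min as the limit for a stable reading. To reach it, the net change between scheduled checks must be 165 to 345 mg/dl. If the two values are independent and normal with SD 60 mg/dl (an assumption), the difference has SD 60√2 = 84.9. The probability of reaching that change is then 5.2% for the 165-minute gap and 0.005% for the 345-minute gap. Over SDs of 45 to 75 the range is about 0% to 12%.

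**4. Can the grid tell a sensor from noise?** A simulation was run with glucose SD 60 mg/dl, 15-minute rates with SD about 1 mg/dl/min, a 15-minute sensor lag, added sensor noise and 3% meter error. These inputs are assumed. Agreement means rates within 1 mg/dl/min, which is a yardstick and not an error-grid zone limit.

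| How rates are formed | Realistic sensor | Unrelated trace |
|---|---|---|
| 15-minute reference | 82% | 54% |
| Scheduled checks, both rates over the same gap | 100% | 97% |
| Scheduled checks against a local 15-minute CGM slope | 78% | 71% |

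The separation is 28 points with a dense reference, and 3 or 7 points with the scheduled checks.

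**5. Pairs below 70 mg/dl, per volunteer and period.** Expected number = n × p; P(none) = (1 − p)^n.

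- Earlier pediatric closed-loop rate, 0.3–0.4% (section I.c): 30 × 0.003 = 0.09 to 35 × 0.004 = 0.14; 87–91% of volunteers have none.
- Success ceiling, 5% (section VI.d): 30 × 0.05 = 1.5 to 35 × 0.05 = 1.75; 17–22% have none and 1.6–2.9% have five or more.
- Night only (12:00 and 3:45 AM, so 10 pairs) at 5%: 0.5.
- Pooled over 32 volunteers, per arm: 3–4 pairs at 0.3–0.4% and 48–56 at 5%.

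These exclude event-triggered readings. For scale, the alert system's validation (section V.d.iii) prompted 29 extra checks in 48 nights, of which 10 + 14 = 24 were at or near a value below 70. Over five nights that is 5 × 24/48 = 2.5, but in a mixed adult and pediatric cohort.

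**6. Short-interval pairs.** A 15–20 minute recheck at 65 mg/dl has a rate standard error of CV × 65 × √2 / gap. At an assumed meter CV of 3–5% this is 0.14 to 0.31 mg/dl/min, which is usable.

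**7. Exercise MARD.** If the absolute error were a constant 10 mg/dl (an illustration; no such figure is given), MARD would be 10/60 = 16.7% at BG 60 and 10/150 = 6.7% at BG 150, a ratio of 2.5 with no change in the sensor.

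**The case against.** The accuracy reference is every HemoCue value, not just the six or seven scheduled ones. The protocol generates closely spaced readings: 15–20 minute rechecks after mild lows in both arms (section V.e), roughly hourly rechecks after highs (V.d.ii), night alert checks and extra calibration checks (V.d.iii). Under the mild-low rule the first recheck normally comes before any protocol carbohydrate, so such a pair is not necessarily distorted by treatment. It would therefore be too strong to infer that no reference rate can be derived. This stands, but only for a sparse subset selected by lows, highs or alerts. It cannot fill a grid for every volunteer and every range.

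A reader might also infer that the rate grid will falsely look accurate. The documents do not support this as a certainty. It holds if both rates are averaged over the same long gap. With a local CGM slope, a realistic sensor scores 78%, slightly below its 82% with a dense reference, and the plan does not say which method applies. What remains is poor discrimination either way.

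Nor does exercise MARD share the sampling defect. It needs single time-matched pairs, and section VI.b foresees readings during exercise. No clock times are given for activity periods, so whether any scheduled check falls within one cannot be settled. That exercise readings cluster at low glucose is plausible, since symptoms prompt checks, but it is not shown.

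The 0.1 figure comes from earlier pediatric closed-loop data and may be too low for usual care or for the oldest volunteers. Pooled point accuracy is workable at about 5% low values.

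**Conclusion.** The concern holds for the rate grid and for low-range results per volunteer. With scheduled checks about 165 to 345 minutes apart, a meaningful reference rate cannot be formed from them. Applied to all pairs, the grid separates a realistic sensor from an unrelated trace by 3 to 7 percentage points, against 28 with a 15-minute reference. Accuracy below 70 mg/dl for a single volunteer rests on roughly 0.1 to 1.75 scheduled pairs per period, before event-triggered checks.

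The gaps depend on the camp timetable and an assumed 20-minute lead. The agreement percentages depend on the simulation's assumed inputs, and their contrast matters more than their exact values. The exercise comparison is a lesser point about possible selection; the number of exercise pairs cannot be computed from the documents.

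A reader should not extend this to the trial's main conclusions. The co-primary endpoints and the success criteria use none of these outputs, and point error-grid results, MARD and MAD remain interpretable when pooled. A change is worth making because the plan states an analysis that its own sampling does not support.

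**What to change.** In section VI.b, CGM secondary analyses:

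- Drop the rate error grid. Alternatively, restrict it to HemoCue pairs within a short maximum gap stated in advance, state how both rates are computed, and report it pooled, with pair counts, as an event-selected subset.
- Keep the point error grid.
- Report range-specific accuracy pooled over volunteers with clustering by volunteer, with the number of pairs and of contributing volunteers, and not volunteer by volunteer.
- Define which fingersticks count as exercise readings. Compare exercise with non-exercise accuracy within the glucose ranges already listed, showing MAD beside MARD and pair counts, and say that the exercise readings are likely to be unscheduled.

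The cost is a change of wording in the analysis plan and the loss of one per-volunteer output. No extra fingersticks or changes to conduct are needed.
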